8.3.5 ADVERSE EVENT REPORTING

Events will be documented accordingly and reported to Northwell Health's IRB.

8.3.6 SERIOUS ADVERSE EVENT REPORTING

The study investigator shall complete an Unanticipated Adverse Device Effect Form and submit to the study sponsor and to the reviewing Institutional Review Board (IRB) as soon as possible, but in no event later than 10 working days after the investigator first learns of the effect. The study sponsor is responsible for conducting an evaluation of an unanticipated adverse device effect and shall report the results of such evaluation to the Food and Drug Administration (FDA) and to all reviewing IRBs and participating investigators within 10 working days after the sponsor first receives notice of the effect. Thereafter, the sponsor shall submit such additional reports concerning the effect as FDA requests.

8.3.7 REPORTING EVENTS TO PARTICIPANTS N/A

8.3.8 EVENTS OF SPECIAL INTEREST N/A

8.3.9 REPORTING OF PREGNANCY N/A

8.4 UNANTICIPATED PROBLEMS

8.4.1 DEFINITION OF UNANTICIPATED PROBLEMS (UP)

The Office for Human Research Protections (OHRP) considers unanticipated problems involving risks to participants or others to include, in general, any incident, experience, or outcome that meets all of the following criteria:

- Unexpected in terms of nature, severity, or frequency given (a) the research procedures that are described in the protocol-related documents, such as the Institutional Review Board (IRB)approved research protocol and informed consent document; and (b) the characteristics of the participant population being studied;
- Related or possibly related to participation in the research ("possibly related" means there is a reasonable possibility that the incident, experience, or outcome may have been caused by the procedures involved in the research); and
- Suggests that the research places participants or others at a greater risk of harm (including physical, psychological, economic, or social harm) than was previously known or recognized. This definition could include an unanticipated adverse device effect, any serious adverse effect on health or safety or any life-threatening problem or death caused by, or associated with, a device, if that effect, problem, or death was not previously identified in nature, severity, or degree of incidence in the investigational plan or application (including a supplementary plan or application), or any other unanticipated serious problem associated with a device that relates to the rights, safety, or welfare of subjects (21 CFR 812.3(s)).

8.4.2 UNANTICIPATED PROBLEM REPORTING

The investigator will report unanticipated problems (UPs) to the reviewing Institutional Review Board (IRB) and to the Data Coordinating Center (DCC)/lead principal investigator (PI). The UP report will include the following information:

- Protocol identifying information: protocol title and number, PI's name, and the IRB project number;
- A detailed description of the event, incident, experience, or outcome;
- An explanation of the basis for determining that the event, incident, experience, or outcome represents an UP;
- A description of any changes to the protocol or other corrective actions that have been taken or are proposed in response to the UP.

To satisfy the requirement for prompt reporting, UPs will be reported using the following timeline:

- UPs that are serious adverse events (SAEs) will be reported to the IRB and to the DCC/study sponsor within <insert timeline in accordance with policy> of the investigator becoming aware of the event.
- Any other UP will be reported to the IRB and to the DCC/study sponsor within <insert timeline in accordance with policy> of the investigator becoming aware of the problem.
- All UPs should be reported to appropriate institutional officials (as required by an institution's written reporting procedures), the supporting agency head (or designee), and the Office for Human Research Protections (OHRP) within <insert timeline in accordance with policy> of the IRB's receipt of the report of the problem from the investigator.

An investigator shall submit to the sponsor and to the reviewing Institutional Review Board (IRB) a report of any unanticipated adverse device effect occurring during an investigation as soon as possible, but in no event later than 10 working days after the investigator first learns of the effect (21 CFR 812.150(a)(1)), A sponsor who conducts an evaluation of an unanticipated adverse device effect under 812.46(b) shall report the results of such evaluation to the Food and Drug Administration (FDA) and to all reviewing IRB's and participating investigators within 10 working days after the sponsor first receives notice of the effect. Thereafter the sponsor shall submit such additional reports concerning the effect as FDA requests (21 CFR 812.150(b)(1))

8.4.3 REPORTING UNANTICIPATED PROBLEMS TO PARTICIPANTS N/A

9 STATISTICAL CONSIDERATIONS

9.1 STATISTICAL HYPOTHESES

• **Primary Efficacy Endpoint(s):** The primary efficacy endpoint is the **POSAS observer scale total score**, evaluated at the 3-month follow-up visit (detailed in Section 9.4.2). The Mann-Whitney U test will be used to assess the superiority of porcine xenograft to second intention healing with respect to this endpoint. A two-sided hypothesis test will be used.

 H_0 : The distributions of POSAS observer scale total score are equal for patients treated with porcine xenograft and second intention healing. H_1 : The distributions of POSAS observer scale total score are not equal for patients treated with porcine xenograft and second intention healing.

- Secondary Efficacy Endpoint(s): The Mann Whitney U test will be used to assess the superiority of porcine xenograft to second intention healing for each of the secondary endpoints below. Additional details for each endpoint are provided in Section 9.4.3. Two-sided hypothesis tests will be used.
- 1. **POSAS patient scale total score**, evaluated at the 3-month follow-up visit by study participants.
- 2. **Healing time**, measured in weeks based on patient's responses to question 1 of the weekly follow-up questionnaire.
- 3. Ratio of scare size to initial defect size
- 4. Pain score at 1 week following surgery
- 5. Number of weeks with pain score above 1

9.2 SAMPLE SIZE DETERMINATION

A total of 50 patients (25 per group) will be recruited in order to ensure adequate power to compare groups on the primary efficacy endpoint, POSAS observer scale total score. Based on a two-sample t-test, a total sample size of 38 will provide 80% power to detect a significant difference between groups, assuming a true difference of 6 points, pooled standard deviation of 6.5 [20], and an alpha level of .05. Given that the asymptotic relative efficiency (ARE) of the Mann-Whitney U test relative to the two-sample t-test is no less than 0.864 [21], regardless of the underlying distribution, a sample size of 44 (38/0.864) will achieve equal power. In order to account for 10% attrition, we will recruit a total of 50 patients.

The assumed difference of 6 points was based on the PI's clinical judgment of the minimal clinically important difference for the POSAS observer scale, which ranges from 6 to 60. It was also informed by previous research which considered 6 points the minimal clinically important difference when comparing second intention healing to an alternative closure method. [20] The mean POSAS observer score among patients treated with second intention healing was estimated at 19.9 in this prior study. Based on this estimate, an improvement of 6 points or more would correspond to a mean POSAS score of 13.9 or lower for patients treated with porcine xenograft.

9.3 POPULATIONS FOR ANALYSES

A modified intention to treat analysis will be performed. All patients will be analyzed according to randomized treatment assignment, unless a patient prefers an alternative treatment method between the time he/she is randomized and the procedure (in which case the patient will be excluded from the study). The **Modified Intention-to-Treat (mITT) Population** will consist of all patients who receive the study intervention and show up for the 3-month office visit follow-up, during which the primary endpoint is evaluated. The Modified Intention-to Treat Population will also include patients who required the rescue therapy, and had the primary endpoint assessed at a follow-up visit when the wound had completely healed. This population will be used to analyze the primary endpoint and all secondary endpoints.

The **Safety Population** will consist of all patients who receive the randomized study intervention. This population will be used to analyze all safety endpoints.

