Block randomization will be used to ensure balance in the number of patients allocated to each treatment group. The randomization schedule will be uploaded to REDCap by a statistician outside of the study team. The PI, who will screen eligible subjects, will not have user rights for the Randomization Setup module within REDCap, and will thus be blinded to which treatment arm is next on the randomization list. Due to the nature of the treatment, it will not be possible to blind the patients. Patients will be asked not to inform the blinded physician observers which treatment they received. The PI will use the "Randomize" button within REDCap to assign patients to porcine xenograft or second intention healing after they have been consented and enrolled in the study.

Prior to intervention the defect size will be measured in terms of length and width using a sterile ruler.

After procedure completion wound care instruction will include daily dressing changes and application of petroleum jelly using a cotton tipped applicator to the wound daily until it is healed.

Weekly questionnaires will be given to the patients by phone or email follow-up. All complications and adverse events would be monitored and recorded for both study groups. Assessment of the scar will be blinded in nature.

The mode of treatment for participants will remain consistent throughout the 3-month period, as both methods are reliable for this type of defect. It is not general practice to place a xenograft on a wound healing by second intention or to remove a xenograft after one has been placed to switch to second intention. Should there be any complications, a modified intention to treat principle, described in Section 9, will be adhered to.

The scars for both study groups will be measured at a single follow up visit after 3 months \pm 1 month, and two blinded investigators will then assess the scar for the primary efficacy endpoint at this time. The blinded evaluators will be other MDs not involved in the study who are working in the dermatology department. The Principle Investigator will speak with the physician to outline what needs to be recorded for each patient. The validated physician observer scar assessment instrument (POSAS) will be used for this purpose. Scar size will consist of a length x width measurement using a ruler.

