5.4 STRATEGIES FOR RECRUITMENT AND RETENTION

Patients scheduled for cutaneous surgery at the Northwell Health Dermatology Clinics at Lake Success and Bay Shore will be approached by the research staff to see if they are interested in participating in the study. A pre-operative surgical consultation for lower extremity cutaneous malignancies is not standard of care. As such, many dermatologic surgery patients receive same-day consult and surgery. Thus it is, in the majority of cases, not feasible to obtain consent prior to the day of surgery. It would pose a burden on the patient and surgeon and may result in delay of surgical care to require a preoperative surgical consultation prior to treatment of lower extremity cutaneous malignancies.

Patients will not be encouraged nor coerced in any way. We do not plan to advertise this study, as the patient population in the department will produce sufficient opportunities to identify patients. Subjects are not compensated for participation in this study.

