6.4 STUDY INTERVENTION COMPLIANCE

Porcine xenograft placement and second intention healing are methods of healing that are currently used and is the patient's and physician's choice. Administration of either porcine xenograft or second intention is part of the standard of care and will be completed as such. An initial visit form will be completed to log the method of treatment administered and will be reviewed to ensure that the randomized treatment was completed.

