6.5.1 RESCUE MEDICINE

The study sites will supply the topical application of rescue medication that will be obtained locally. The following rescue medications may be used:

Silver Nitrate Wood Applicator Sticks Henry Schein Model: 1126994

The use of rescue medication is allowable after the formation of hypergranulation tissue which may begin to occur 6-8 weeks post-operatively, but typically the use of rescue medications should be delayed, if possible, for at least 10-12 weeks following the surgical date. This is considered standard of care, as it allows the patient the chance to heal without adjunct medication. The date and time of rescue medication administration as well as the name and regimen of the rescue medication will be recorded in RedCAP. Follow-up after the application of the rescue medication will occur every 6 weeks or until healed, per our surgical standard of care.

For patients receiving rescue medication, the POSAS observer scale total score (primary outcome), POSAS patient scale total score (secondary outcome), and ratio of scar size to initial defect size (secondary outcome) will be recorded at the patient's follow-up visit within 6 weeks of administering the rescue medication, or at a subsequent follow-up visit when the wound is fully healed. (Note that it is not possible to administer the POSAS instrument, a scar assessment tool, if the wound is not completely healed).

As described in Section 9.3, a modified intention-to-treat analysis will be used, in which all patients who have been assessed for the primary study endpoint will be analyzed according to their randomized treatment group.

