9.4.2 ANALYSIS OF THE PRIMARY EFFICACY ENDPOINT(S)

1. **POSAS observer scale total score.** The primary efficacy endpoint will be the total score of the POSAS observer scale, assessed at the 3-month follow-up visit by two blinded evaluators who will not be involved in the placement of the porcine xenograft. For each patient, scores from the two blinded investigators will be combined by calculating the mean. The POSAS (Patient and Observer Scar Assessment Scale) is a validated assessment tool used for the assessment of all types of scars by professionals and patients [17-19]. The observer scale is comprised of 6 items (vascularity, pigmentation, thickness, relief, pliability, and surface area) scored on a scale from 1("like normal skin") to 10 ("worst scar imaginable"). The total score is calculated as the sum of the six items (range, 6-60). This is a subjective endpoint, given that it is based on the evaluating physician's judgment of each scale item.

All patients will be evaluated by two blinded observers, who will be selected from the other attending physicians and/or resident physicians at the site. However, all patients will not be evaluated by the same set of observers due to differences in physician schedules. Agreement between the blinded evaluators will be assessed using the intraclass correlation coefficient (ICC). The form of the ICC will be the ICC(1,2).

Statistical Analysis: The Mann Whitney U test will be used to compare the two study arms on the primary efficacy endpoint based on the mITT Population defined in Section 9.3. No adjustments for multiplicity will be made because there is only one primary endpoint, and this endpoint will not be evaluated during the planned interim safety analysis.

We will summarize the POSAS observer scale score for the two study arms using the mean (SD), and median (IQR). As a measure of effect size between the porcine xenograft and second intention healing groups, we will calculate the Hodges-Lehmann estimate of the median difference, and corresponding 95% confidence interval. This is equal to the median of all paired differences between observations in the porcine xenograft and second intention healing groups.

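### Section 9.3 drops unblinded patients who decline their allocated method before the procedure, so the only efficacy population permits selection that depends on arm

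*Combined protocol and SAP*

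**What the plan says.** Section 9.3 (Populations for Analyses) keeps patients in their randomised arm with one exception: a patient who "prefers an alternative treatment method between the time he/she is randomized and the procedure (in which case the patient will be excluded" from the study). It defines the mITT population as "all patients who receive the study intervention and show up for the 3-month office visit follow-up", and extends it to rescue patients who are scored once healed. This population serves the primary and all secondary endpoints. Section 9.4.2 confirms it for the primary test: "The Mann Whitney U test will be used to compare the two study arms on the primary efficacy endpoint based on the mITT Population".

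Section 6.5.1, which refers back to Section 9.3, summarises the same analysis without either condition: "all patients who have been assessed for the primary study endpoint will be analyzed according to their randomized treatment group".

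Three other places bear on how the rule would operate:

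- Section 4.1: "Due to the nature of the treatment, it will not be possible to blind the patients". The same section says that, outside the trial, surgeon and patient choose between the methods.
- Section 6.4 describes the two arms as "methods of healing that are currently used", and adds a record of what was done: "An initial visit form will be completed to log the method of treatment administered".
- Section 5.4: "many dermatologic surgery patients receive same-day consult and surgery", so consent before the day of surgery is mostly not feasible.

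**The concern.** Randomisation makes the arms comparable at the moment of allocation. A rule that removes patients after they know their allocation, for a reason that allocation can influence, may undo this. A patient allocated to one method can prefer the other, and the other is available in ordinary practice. If those who decline differ in prognosis from those who accept, and decline more often in one arm, the remaining patients are no longer comparable. Concealed allocation and blinded evaluators do not protect against this, because the selection happens after allocation is revealed and before any score is taken.

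What is at stake is the trial's single confirmatory comparison. The number of refusals could be recovered from the REDCap allocation and the initial visit form, but the plan does not commit to reporting it by arm. The effect of refusals on the result could not be recovered: no 3-month score is planned for these patients, and Section 9.4 has no sensitivity analysis for randomised patients without a primary score.

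**Working it through.** **1. Does anything else in the plan retain these patients?**

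- Section 7.1 keeps patients in the study after the xenograft is discontinued, and Section 7.2 applies intention to treat to graft removal or failure. Both concern events after placement.
- The rescue extension in Section 9.3 concerns treated patients.
- The Safety Population requires receipt of the randomised intervention.
- Sections 9.4.1 to 9.4.9 define no other efficacy set and no missing-data analysis.

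A refusal between allocation and procedure is therefore not retained anywhere.

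**2. The plan's own sample size (Section 9.2).** Inputs: difference 6 points, SD 6.5, two-sided alpha 0.05, power 80%, ARE 0.864, attrition 10%.

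- Normal approximation: n per arm = 2 × (1.960 + 0.842)² × (6.5/6)² = 18.4, rounded up to 19, so 38 in total. This matches the plan.
- 38/0.864 = 43.98, so 44. This matches.
- 44/0.90 = 48.9, so 49. The plan recruits 50, which gives 25 per arm.
- By the noncentral t distribution, power at 19 per arm is 0.791. This is the baseline below.

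The 10% attrition has no separate allowance for refusals.

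**3. Size of a possible bias.** The documents give neither the number of refusals nor their prognosis, so both are assumed. Let f be the fraction of one arm of 25 that declines, and d the difference in expected score between those who decline and those who stay. Removing them shifts that arm's mean by f × d. Type I error and power come from the noncentral t with SD 6.5 and effective N = 44 × 0.864 = 38.0.

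| Refusals, all in one arm | d (points) | Shift f × d | Type I error | Power at a true 6, shift against / in favour |
|---|---|---|---|---|
| any number | 0 | 0 | 5.0% | 0.791 (before loss of numbers) |
| 1 | 6.5 | 0.26 | 5.2% | 0.755 / 0.824 |
| 2 | 3.25 | 0.26 | 5.2% | 0.755 / 0.824 |
| 3 | 3.25 | 0.39 | 5.4% | not computed |
| 2 | 6.5 | 0.52 | 5.7% | 0.715 / 0.853 |
| 3 | 6.5 | 0.78 | 6.5% | 0.673 / 0.879 |

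Shifts of 0.52 and 0.78 are 9% and 13% of the 6-point target.

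**4. Cross-checks with the planned test.**

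- Mann-Whitney simulation (200,000 runs, normal scores, refusers 1 SD different). With 25 per arm, rejection under the null is 4.8%, 5.1%, 5.6% and 6.6% for 0, 1, 2 and 3 removed. With 22 per arm it is 5.0%, 4.8%, 5.4% and 6.3%.
- A different selection model (20,000 runs) removes the k patients with the worst expected prognosis from one arm. With a correlation of 0.5 between expected and actual score, k = 2 gives a shift of about 0.5 points and 5.8%; k = 5 gives 1.1 points and 8.2%. With a correlation of 0.3, the figures are 0.3 points and 5.0%, and 0.7 points and 6.1%.

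**5. Length of the window.** With same-day consult and surgery, the interval from allocation to procedure lies within the day for most patients. The Synopsis and Section 2.2 place randomisation once surgery is finished, which would make it shorter still. The Schedule of Activities marks it only under Screening, although eligibility depends on the post-operative defect and on linear closure not being recommended. Section 4.1 (after consent and enrolment) fits either reading.

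**The case against.** The strongest counter-argument is that the effect is probably small. The window is short, perhaps minutes if randomisation follows surgery. Changes of mind after placement are already handled by Sections 7.1 and 7.2. Type I error passes 5.5% in the table only with two or more refusals, all in one arm and a full SD different. The power figures use the worst-case ARE of 0.864; at the normal-theory value of about 0.955, the baseline is 0.83 and the adverse range 0.72–0.76. All of this stands, and it limits the severity. It does not remove the rule: the plan sets no cap on refusals and collects nothing that would show afterwards whether they were harmless.

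Second, Section 6.5.1 defers to Section 9.3 and sits in the rescue section, so it is shorthand and not a rival definition. That is a fair reading. The two descriptions still differ and should be aligned.

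Third, the mITT definition asks for receipt of the study intervention, while the Safety Population specifies the randomised one. On that reading a patient who crosses to the other method would meet the mITT receipt condition, and the preference clause alone would remove them. This is arguable, but the preference clause is enough for the concern.

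Fourth, no-shows, safety counting and randomisation timing are separate matters. They are; the concern does not depend on them.

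**Conclusion.** The concern holds. As written, Section 9.3 permits exclusion after randomisation that can depend on the arm, in the only population used for the primary test, and nothing else in the plan brings those patients back. Whether bias would arise, and in which direction, cannot be known from the documents. If refusal is unrelated to prognosis there is no bias, only fewer patients. Under the assumed values the range runs from negligible (one refusal, 5.2%) to modest (two to three refusals in one arm at 1 SD: 5.7–6.5% type I error, with power moving from 0.79 to 0.67–0.72 or 0.85–0.88 by direction). This should be fixed because the change is cheap and the loss of comparability could not be assessed later, not because a large distortion is expected.

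**What to change.** 1. In Section 9.3, delete the preference exclusion and the receipt condition, so that every randomised patient with a primary assessment is analysed in the randomised arm. This agrees with the description in Section 6.5.1. State how patients who switch are counted in the Safety Population.
2. Ask patients who decline their arm to attend the same 3-month visit with the same blinded scoring.
3. Report refusals, switches and missing primary scores by arm, using the allocation record and the initial visit form.
4. For randomised patients without a primary score, pre-specify a bounding analysis: shift assumed scores over a stated range (for example ±6.5 points) until the conclusion changes, with the scale limits 6 and 60 as outer bounds. This also covers no-shows, whom Section 7.3 withdraws.
5. Reconcile the Schedule of Activities with the Synopsis and Section 2.2, so that randomisation follows confirmation of post-operative eligibility and of willingness to accept either arm. This should reduce refusals at source.

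**Cost.** A short amendment and no extra recruitment. Some decliners will also decline follow-up, so bias is reduced and not removed; one of 25 still missing at 1 SD leaves type I error at 5.2%. Retained switchers dilute the effect: with 2 or 3 of 25 in one arm, 6 × (1 − 2/25) = 5.52 and 6 × (1 − 3/25) = 5.28 points, with power about 0.72 and 0.68 at 44 evaluable and ARE 0.864. On power alone that is no better than the adverse-bias case; the gain is validity.

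The bounds widen as scores go missing. In a simulation (4,000 runs, means 13.9 and 19.9 from Section 9.2, SD 6.5, scores clipped to 6–60, 25 randomised per arm, missing counts assumed), the mean Hodges-Lehmann estimate is about 5.8. With two missing in one arm it spans about 5.4–6.3 (±6.5 points) or 4.9–6.6 (scale limits). With three and two missing it spans 4.6–6.9 or 3.2–7.9.

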9.4.4 SAFETY ANALYSES

Safety Endpoints:

1. **Infection.** Patient's charts will be reviewed at the completion of their 3-month office visit follow-up in order to analyze if they visited the dermatologist between the date of surgery and 3-month office visit and if infection was diagnosed.

2. **Bleeding**. During each of the weekly follow-up questionnaires and during the 3-month follow-up visit, patients will be asked if they have experienced any post-operative bleeding that led to a visit to the physician (yes/no) and if there was any intervention performed by the physician to stop the bleeding (yes/no). Bleeding will be considered an adverse event if an intervention by a physician was required to stop the bleeding. The number and percentage of patients who experienced bleeding at any time during the 3-month follow-up period will be reported.

3. **Pain**. The proportion of patients with a pain score ≥ 6 at the operative site will be assessed at one week following surgery. This will be based on the patient's response to the weekly follow-up questionnaire, with scores ranging from 1 (no pain) to 10 (worst imaginable pain).

Statistical Analysis: We will report the frequency and proportion of patients experiencing each of the safety endpoints above, based on the Safety Population defined in Section 9.3. The proportion of patients experiencing each type of complication (infection, bleeding, pain) will be compared between porcine xenograft and second intention healing using Fisher's exact test.

In addition to the planned safety analysis at the completion of the study, one interim analysis will be conducted by the study statistician after 26 patients have been randomized and complete the final study visit at 3 months post-intervention. This is equal to approximately 50% of the planned enrollment goal of 50 patients. The purpose of this interim analysis will be to review the safety endpoints. There will be no formal stopping rule based on the statistical significance of the interim safety analysis. The principal investigator will alert the IRB immediately if there is any evidence or suggestion of a difference between treatment groups with regard to AEs or SAEs. Additional details on this interim safety analysis are included in Section 9.4.6.

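### The Safety Population in 9.3 admits only patients who got their randomized method, so a patient given the other method for a non-preference reason drops out of the infection, bleeding and high-pain comparisons

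*Combined protocol and SAP*

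**What the plan says.** Section 9.3 defines two analysis sets with different treatment conditions.

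- The mITT population "will consist of all patients who receive the study intervention and show up for the 3-month office visit follow-up". It is used for the primary and all secondary endpoints, and the grouping rule is "All patients will be analyzed according to randomized treatment assignment".
- The Safety Population "will consist of all patients who receive the randomized study intervention". It does not require the 3-month visit, but it does require that the method given was the one allocated. No grouping rule is stated for it.

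Section 9.3 has one exception, which applies "unless a patient prefers an alternative treatment method between the time he/she is randomized and the procedure". The consequence is exclusion: "in which case the patient will be excluded from the study".

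Section 6.5.1 restates the mITT rule without any condition on the method received: "all patients who have been assessed for the primary study endpoint will be analyzed according to their randomized treatment group".

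Section 9.4.4 reports the three safety endpoints and compares them by Fisher's exact test "based on the Safety Population defined in Section 9.3". Section 6.4 provides the variable that would show a mismatch: "An initial visit form will be completed to log the method of treatment administered". That form is then checked against the allocation, but no section says how a mismatch is handled in the analysis.

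**The concern.** Safety comparisons are meant to describe what happens to patients exposed to each method. A set that requires the allocated method to have been given removes a treated patient because of what happened at the procedure, after randomization. The reason for departing from the allocation may be connected with the wound itself.

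Take a patient allocated to second intention who is given a xenograft by surgeon decision or error. An infection or a bleed on that graft enters neither arm of the 9.4.4 comparison, although the patient was exposed to the device under study. The same patient may still supply a primary endpoint value under second intention. The week-1 pain score could then count as a secondary endpoint while its dichotomized form is left out as a safety endpoint.

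The interim review in 9.4.6 has no formal stopping rule. It relies on the principal investigator seeing any suggestion of a difference between arms, so it should be clear beforehand whose events are counted.

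**Working it through.** **Step 1: the planned size, used below as the denominator.** From 9.2: difference 6, SD 6.5, two-sided alpha 0.05, power 80%. The normal approximation gives 2 × (1.960 + 0.842)² × 6.5² / 6² = 18.4, so 19 per arm and 38 in total. Then 38 / 0.864 = 43.98, so 44, and 44 / 0.90 = 48.9, so 49, or 50 with equal arms. The plan's 50 (25 per arm) is reproduced. The point does not depend on it.

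**Step 2: membership by case, from the wording of 9.3, 6.5.1 and 7.2.**

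| Case | mITT | Safety |
|---|---|---|
| (a) Patient prefers the other method before the procedure | Out (excluded from the study) | Out |
| (b) Other method given for another reason; mITT treatment condition read as either method | In, under the randomized arm, if assessed | Out |
| (c) As (b), but mITT treatment condition read as the assigned method | Out | Out |
| (d) Xenograft placed as allocated, later removed or failed (7.2) | In, if assessed | In |

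Cases (b) and (c) agree on Safety: the patient is out. They differ only on mITT. Two features favour reading (b). The word *randomized* appears in the Safety definition and not in the mITT definition. And 6.5.1 takes everyone assessed for the primary endpoint, by randomized group. Section 9.3 does not say so outright.

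**Step 3: effect on the denominators.** The documents give no rate of non-preference switches. Assume k = 0 to 3 patients (up to 3/50 = 6%) allocated to xenograft receive second intention; the opposite direction is the mirror image.

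| k | Safety set as written (xenograft/second intention) | All treated, by method received |
|---|---|---|
| 0 | 50 (25/25) | 50 (25/25) |
| 1 | 49 (24/25) | 50 (24/26) |
| 2 | 48 (23/25) | 50 (23/27) |
| 3 | 47 (22/25) | 50 (22/28) |

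**Step 4: expected events.** Section 8.3.2 gives a complication rate of 1.6%.

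- All 50 patients: 50 × 0.016 = 0.8.
- The 26 patients at the interim: 26 × 0.016 = 0.42.
- Among 1 to 3 off-allocation patients: 0.016 to 0.048.
- Chance of at least one event among them: 1 − 0.984 = 1.6% for one patient, and 1 − 0.984³ = 4.7% for three.

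The 1.6% refers to complications such as haemorrhage, necrosis, infection and dehiscence. It does not cover week-1 pain at the high cut-off, for which the documents give no rate. These figures therefore do not describe the pain endpoint.

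**The case against.** The strongest reply is that the case is hypothetical and little is lost. One surgeon treats everyone, allocation is by REDCap, and the visit form is reviewed against the allocation. The one switch the plan foresees, patient preference, leads to exclusion from the study and so from both sets. All of this stands, and it limits how often the gap could matter. It does not close it: a surgeon's decision or an error is covered nowhere.

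A reader might infer that such a patient's complications vanish from the trial. The documents do not support that. Sections 4.1 and 8.3.4 have complications and adverse events recorded for everyone on study. The interim comparison of serious adverse events in 9.4.6 names no population, so exclusion there is not shown. If the patient is in mITT, week-1 pain and the number of weeks with pain are still compared as secondary endpoints.

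A reader might also take it as settled that the patient is in the efficacy set. That rests on reading (b), which is the more natural reading but is not stated.

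Nor is it an error in itself that the two sets do not nest. The Safety Population is rightly wider in that it does not require the 3-month visit.

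Finally, an omitted event would rarely alter a test result. With 1/25 against 0/25, Fisher's two-sided p is 1, and with no events there is no difference to test. What would change is the description: one observed event becomes none.

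**Conclusion.** The point holds in a limited form. As written, 9.3 and 9.4.4 leave a patient given the other method for a non-preference reason out of the infection, bleeding and high-pain comparisons, whichever way the mITT wording is read. That the patient also stays in the efficacy analysis depends on reading the mITT treatment condition as either method.

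The likely numerical effect is small: probably zero to a few such patients, with 0.016 to 0.048 expected complications among an assumed 1 to 3 at the 1.6% rate. The number of patients is an assumption, and the rate does not cover pain. Sample size, the primary test and the primary analysis set are unaffected. This is a minor correction, best made before the interim analysis so that nobody has to decide afterwards whose complications count.

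**What to change.** In 9.3, replace the Safety Population sentence with: *The Safety Population consists of all enrolled patients who have either method applied at the study procedure, grouped by the method actually received as logged on the initial visit form (6.4).*

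Four further statements are needed:

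1. This population is used for the interim analysis in 9.4.6, including the comparison of serious adverse events, and for the final analysis in 9.4.4.
2. The method received is supplied to the statistician under the same masked A/B coding as the allocation. Sections 6.3 and 9.4.6 now describe only one treatment-group label.
3. Patients who switch by preference before the procedure are either in or out of the Safety Population. Section 9.3 now excludes them from the study, and the new sentence would otherwise leave their status unclear.
4. The treatment condition in the mITT definition means either method. mITT stays grouped by randomized arm.

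The cost is a few sentences in 9.3 with cross-references, and one extra masked variable in the data transfer. The method received is already collected. The downside is that safety and efficacy group sizes may differ by one or two patients, which a footnote to the safety table can explain.
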